**IRB-41878**

**ENT0066**

**NCT03733210**

[REDACTED]

Relevant US FDA submissions:

$^{89}\text{Zr}$ -panitumumab: **IND 135573**, [name] (IND-holder)  
(*NCI's IND 116229 is incorporated by cross-reference*)

Panitumumab-IRDye800: IND 119474, incorporated by cross-reference  
([name])

Cetuximab-IRDye800: IND 115706, incorporated by cross-reference  
([name])

IRDye800 Master File MF-25167, incorporated by cross-reference  
(LI-COR Biosciences, Inc)

SRC approval date:

03 April 2018

Version date	Document History
12 Jun 2017	Full draft, for initial IRB and pre-IND submission
20 Dec 2017	Initial Version – IRB/FDA/SRC
26 Mar 2018	Final SRC Comments
08 Jun 2018	Initial IND submission
07 Jul 2018	Received “Study may proceed” from FDA
04 Sep 2018	IRB approval granted for the study
01 Mar 2019	
Protocol modifications:
 
 
- Personnel update: Added [name] as CRC, [name] as statistician (substituting previous statistician [name]), and [name] as co-investigator
 
- Clarify language regarding study procedures (section 9)
 
- Addition Appendix C that includes a device list used for detection/imaging of Zr-panitumumab
 

12 Apr 2019	
Protocol modifications:
 
 
- Removal of “Received an investigational drug within 30 days prior to first dose of panitumumab-IRDye800” as an exclusion criterion (section 3.2 and Appendix A).
 
- Addition of correlative studies for primary tumor assessment (section 8).
 
- Addition of collection of vital signs just before infusion of the Zr-panitumumab bolus infusion (section 9.2.2)
 
- Updated Appendix C with in-house developed 1mm resolution mobile PET system (collaboration with dr. [name], Radiology).
 

17 Sep 2019	
Protocol modifications:
 
 
- Extension of window of PET/CT from Day 0 to the Day before Surgery.
 
- Inclusion of dosimetry sub-study (3-5 subjects) to collect dosimetry data that will provide insight on Zr-panitumumab toxicity data.
 
- Clarification on Day 15 and Day 30 study procedures.
 
- Personnel updates: Removed [name] as co-investigator.
 
- Administrative changes to the protocol document.
 

13 Jan 2020	
 
- Removal [name] as CRC, addition of [name] as CRC
 

20 Apr 2020	
Dose modification of panitumumab-IRDye800
 
Revisions to Appendix B include:
 
 
- Addition of investigational device "OnLume Imaging System"
 
- Removal of investigational device “PDE-NEO II”
 

8 May 2020	
 
- Removes investigational device "OnLume Imaging System," erroneously identified as the intraoperative near-infrared fluorescence imaging device “Asimov 7685”
 
- Adds investigational device “PDE-NEO II” back to protocol.
 
- Add identifiers for IND number and NCT number
 

19 Aug 2021 (also in 6 Aug 2020 versions)	
Protocol modifications (non-significant change) – Addition of investigational device:
 
 
- “IMAGE1 S RUBINA System” for evaluation of excised tissue only, not for treatment decisions
 

19 Aug 2021 (also in 23 Apr 2021 / 5 April 2021 versions)	
Protocol modifications:
 
 
- Clarified expected Adverse Event collected window to only designated study dates
 
- Cardiac Monitoring, Adverse Event and Serious Adverse Event reporting clarification
 
- Change IND-holder to [name]
 

## PROTOCOL SYNOPSIS

TITLE	Pilot Study Evaluating Panitumumab-IRDye800 and  Zr-Panitumumab for Dual-Modality Imaging for Nodal Staging in Head and Neck Cancer														
STUDY PHASE	Early phase 1 (pilot study)														
INDICATION	Biopsy confirmed diagnosis of squamous cell carcinoma of the head and neck (HNSCC). Subjects diagnosed with any T stage, any subsite within the head and neck that are scheduled to undergo surgical resection. Subjects with recurrent disease or a new primary will be allowed.														
INVESTIGATIONAL PRODUCT	
Zr-panitumumab and panitumumab-IRDye800.
 
This study seeks to determine if the combined use of Zr-panitumumab and panitumumab-IRDye800 can be used to identify tumor-loaded lymph nodes in subjects with HNSCC who undergo surgery with curative intent. The table below summarizes the planned dose level.
 
  
 Dosing Schedule	
   
 No of subjects	14	
 
 Dose of panitumumab-IRDye800	30 mg	
 
 Dose of Zr-panitumumab	1.0 mCi, allowable range: 0.8 to 1.2 mCi (29 to 45 Mbq)	
 
 Specific Activity of Zr-panitumumab	> 200 Ci/mmol	
 
 PET imaging post-injection	Day 0 to Day before Surgery	
 
 Timing of intraoperative imaging and surgical procedure post-injection	Day 2 to 5 post-infusion	
  
	Dosing Schedule		No of subjects	14	Dose of panitumumab-IRDye800	30 mg	Dose of  Zr-panitumumab	1.0 mCi, allowable range: 0.8 to 1.2 mCi (29 to 45 Mbq)	Specific Activity of  Zr-panitumumab	> 200 Ci/mmol	PET imaging post-injection	Day 0 to Day before Surgery	Timing of intraoperative imaging and surgical procedure post-injection	Day 2 to 5 post-infusion
Dosing Schedule															
No of subjects	14														
Dose of panitumumab-IRDye800	30 mg														
Dose of  Zr-panitumumab	1.0 mCi, allowable range: 0.8 to 1.2 mCi (29 to 45 Mbq)														
Specific Activity of  Zr-panitumumab	> 200 Ci/mmol														
PET imaging post-injection	Day 0 to Day before Surgery														
Timing of intraoperative imaging and surgical procedure post-injection	Day 2 to 5 post-infusion														
TREATMENT SCHEDULE	
Subjects receive F-FDG-PET/CT and/or F-FDG-PET/MRI as part of their standard of care prior to study enrollment. After infusion of study agents on Day 0, subjects will undergo Zr-panitumumab PET/CT imaging between Day 0 and the Day before Surgery. Subjects enrolled in the dosimetry sub-study will undergo imaging on day 0 to the day before surgery, for a total of 3 PET/CT scans.
 
Subjects will undergo surgical resection at 2-5 days after infusion (see figure below) based on expected half-life of panitumumab-IRDye800. Imaging will be performed intraoperatively using the optical imaging devices listed in Appendix B and the Zr-detecting/imaging devices listed in Appendix C. The oncologic surgery will be conducted following the standard of care. Ex vivo imaging of the specimen prior to pathological assessment will be performed using non-invasive radioactive and fluorescence imaging modalities that do not violate or destroy the tissue.
														
TREATMENT SCHEDULE	Subjects receive  F-FDG-PET/CT and/or  F-FDG-PET/MRI as part of their standard of care prior to study enrollment. After infusion of study agents on Day 0, subjects will undergo  Zr-panitumumab PET/CT imaging between Day 0 and the Day before Surgery. Subjects enrolled in the dosimetry sub-study will undergo imaging on day 0 to the day before surgery, for a total of 3 PET/CT scans.														

TREATMENT SCHEDULE	
Subjects will undergo surgical resection at 2-5 days after infusion (see figure below) based on expected half-life of panitumumab-IRDye800. Imaging will be performed intraoperatively using the optical imaging devices listed in Appendix B and the <math>^{89}\text{Zr}</math>-detecting/imaging devices listed in Appendix C. The oncologic surgery will be conducted following the standard of care. Ex vivo imaging of the specimen prior to pathological assessment will be performed using non-invasive radioactive and fluorescence imaging modalities that do not violate or destroy the tissue.
  
IV infusion panitumumab-IRDye800 and <math>^{89}\text{Zr}</math>-panitumumab
 
<math>^{89}\text{Zr}</math>-panitumumab PET/CT imaging*
 
Surgery
 
Follow-up**
 
Cohort 1 (n=7: LN-)
 
Cohort 2 (n=7): LN+
 
Day 0
 
Day 0 - Day before surgery
 
Day 2-5
 
Day 15
 
Day 30
 
*Patients (n=3-5) in de dosimetry substudy will receive 3 PET/CT scans between day 0 and day of surgery. **On day 15 patients will come to the clinic. At day 30 patients will be called.

PRIMARY OBJECTIVE(S)	
Determine the sensitivity and specificity of <math>^{89}\text{Zr}</math>-panitumumab for the detection of tumor-involved regional lymph nodes.
 
As defined by histological and/or pathological evaluation (gold standard), the total number of tumor-positive nodes will be determined and correlated to the radiologically-suspicious nodes identified by <math>^{89}\text{Zr}</math>-panitumumab and <math>^{18}\text{F}</math>-FDG contrast agents using PET/CT and/or PET/MRI imaging. The specificity and sensitivity of <math>^{89}\text{Zr}</math>-panitumumab will be calculated and compared to the specificity and sensitivity of <math>^{18}\text{F}</math>-FDG for metastatic lymph node identification.

SECONDARY OBJECTIVE(S)	
Determine the number (proportion) of lymph nodes determined to be tumor-positive by histological and/or pathological evaluation that were NOT predicted tumor-positive by <math>^{89}\text{Zr}</math>-panitumumab.
 
As defined by histological and/or pathological evaluation (gold standard), the total number of tumor-positive nodes will be determined and compared to the <math>^{89}\text{Zr}</math>-panitumumab and <math>^{18}\text{F}</math>-FDG-PET/CT and/or -PET/MRI imaging findings. We will compare the odds of a false negative using <math>^{89}\text{Zr}</math>-panitumumab-PET relative to the odds of a false negative using a <math>^{18}\text{F}</math>-FDG-PET and compare their respective negative predictive values.

EXPLORATORY OBJECTIVE(S)	
 
Determine the sensitivity and specificity of panitumumab-IRDye800 for the detection of tumor-involved regional lymph nodes. After isolation of lymph nodes from the specimen in the pathology lab, lymph node fluorescence will be measured prior to histological and/or pathological evaluation (gold standard). Sensitivity and specificity will be calculated by comparison of fluorescence intensity to histological and/or pathological evaluation (gold standard). Results will be compared to the sensitivity and specificity of Zr-panitumumab and F-FDG (primary objective).
 
Determine the number (proportion) of lymph nodes determined to be tumor-positive by histological and/or pathological evaluation that were NOT predicted tumor-positive by panitumumab-Irdye800. We will compare the odds of a false negative using fluorescence imaging of panitumumab-IRDye800 to the odds of a false negative using Zr-panitumumab-PET and F-FDG-PET and compare the negative predictive values. Additionally, we will test the association of the panitumumab-Irdye800 results to Zr-panitumumab-PET and F-FDG-PET results with the Phi coefficient.
 

SAMPLE SIZE AND DURATION OF STUDY	
It is anticipated that 14 subjects will be enrolled into the study. Safety data and adverse events will be reported at 15 days after the last subject receives the infusion, which is in excess of 4-fold the half-life of the largest dose of pantumumab-IRDye800 (2.3 days) and of the half-life of Zr-panitumumab (3.3 days). Each subject will be followed for 30 days following the last dose of study medication.
 
It is anticipated that the study will require 12 to 18 months to be completed.

STATISTICAL CONSIDERATIONS	
General analysis tools All specimens from both cohorts will be pooled for the primary and secondary analyses. We will use the matched pair Durkalski's test that accounts for the correlation of multiple specimens per patient, to compare the specificity and sensitivity of Zr-panitumumab-PET to F-FDG-PET. We will compare the odds of a false negative with Zr-panitumumab-PET relative to the odds of obtaining a false negative with F-FDG-PET.
 
Approach to drawing statistical inference Significance for all tests will be assessed at the 0.05 level and 95% confidence intervals will be reported and interpreted.
 
Descriptive statistics We will present means and standard deviations (or medians and interquartile ranges when appropriate) for continuous characteristics such as maximum standard uptake values (<math>SUV_{max}</math>) as determined with Zr-panitumumab-PET and F-FDG-PET and radioactivity counts of Zr-panitumumab in the node(s) as determined with the PET probe, and tumor-to-background ratios (TBRs) and mean fluorescence intensity (MFI) for panitumumab-Irdye800. For categorical variables such as drainage pattern and number of lymph nodes visualized, we will present frequency statistics. Graphical tools such as heat maps, histograms, and boxplots will be used to assess distributional properties of continuous variables. We will illustrate the nature of the relationship between <math>SUV_{max}</math>/radioactivity counts and/or MFI/TBRs and/or drainage pattern across all subjects, the relationship will be illustrated with a heat map and spaghetti plot. When appropriate, transformations – including a log-based transformation – may be considered to stabilize variance.

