## **10. MEASUREMENTS**

### **10.1 Primary Outcome Measure**

**The number (proportion) of lymph nodes determined to be tumor-positive by histological and/or pathological evaluation that were predicted to be tumor-positive by  $^{89}\text{Zr}$ -panitumumab labeling.**

We will compare the number and location of  $^{18}\text{F}$ -FDG-avid nodes within the regional lymphatics to the number and location of  $^{89}\text{Zr}$ -panitumumab-avid nodes in relation to the postoperative neck dissection histopathology (gold standard).

**Outcome Measure:** Preoperatively, the location and number of  $^{18}\text{F}$ -FDG-avid nodes as well as the number and location of  $^{89}\text{Zr}$ -panitumumab-avid nodes will be determined by 2 board-certified Nuclear Medicine physicians ([name] and [name]). Once all radioactive and fluorescent nodes are removed intraoperatively, standard of care will be

performed via completion neck dissection. The excised tissue specimens will be sent to pathology where the tumor status of the lymph nodes will be determined (histology serves as our gold standard). This will allow us to determine true and false positive and negative tumor values for Zr-panitumumab and F-FDG in identifying the tumor-loaded lymph nodes.

**Time Frame:** Final false positive and negative rate, sensitivity and specificity of sentinel node detection using Zr-panitumumab can be determined towards the completion of the trials (once all subjects have been included and all the data has been collected).

**Safety Issue:** No

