## **12. STATISTICAL CONSIDERATIONS**

Data from both cohorts (14 subjects) will be combined for all primary and secondary analyses.

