### **Primary objective**

**Determine the sensitivity and specificity of Zr-panitumumab for the detection of tumor-involved regional lymph nodes.**

Using the histological and/or pathological evaluation of the lymph node as the gold standard, we will calculate and compare the sensitivity and specificity of Zr-panitumumab and F-FDG PET/CT imaging findings. We will test the level of association of the Zr-panitumumab-PET results and the F-FDG-PET results with the Phi coefficient.

We will use the matched pair Durkalski's test (36), accounting for the cluster-correlation within subjects, for the sensitivity and specificity comparisons (primary and exploratory) using the clust.bin.pair package (37) in the R-statistical software (39). Significance for both primary and exploratory analyses will be assessed at the 0.05 level and to assess uncertainty, 95% confidence intervals will be provided for all estimates.

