### Sample Size Justification and Power Considerations

Since this is an early Phase I study, power considerations are limited but even so, we have excellent power to detect differences in specificity. With 14 subjects and an average of 30 nodes per subject, we expect 420 specimens on which to calculate and compare sensitivity and specificity. However, in calculating power, we must account for the clustering or correlation of lymph nodes within subject. Although we will use Durkalski's test to compare sensitivities and specificities, we estimated power by first determining the effective sample size (ESS), adjusting for the correlation of LNs within person, and then estimated power using McNemar's test on this ESS. We assumed an intra-class correlation of 0.005, yielding an effective sample size of 367 LNs. With an effective sample size of 367, a prevalence of 7.5%, a significance level of 0.05, and a 0.3 proportion of discordant pairs, we have greater than 95% power to detect a 0.1 difference in specificities, assuming the lower specificity is 0.7. Similarly, we have greater than 71% power to detect a 0.25 difference in sensitivity with the one-sided McNemar test. This assumes the proportion of discordant pairs is 0.3 and the lower sensitivity is 0.7.

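### Durkalski's test weights subjects equally, but the plan's sensitivity and specificity are node-weighted, so with unequal node counts the p-value may not test the pooled difference printed beside it

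*Combined protocol and SAP*

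**What the plan says.** **Unit of the estimate.** The primary outcome measure in Section 10.1 is "The number (proportion) of lymph nodes determined to be tumor-positive by histological and/or pathological evaluation that were predicted to be tumor-positive by" the zirconium tracer. The sample size paragraph of Section 12 reads: "With 14 subjects and an average of 30 nodes per subject, we expect 420 specimens on which to calculate and compare sensitivity and specificity". Both point to node-level proportions.

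**Cohorts.** The Synopsis states "All specimens from both cohorts will be pooled for the primary and secondary analyses", and Section 12 opens with "Data from both cohorts (14 subjects) will be combined for all primary and secondary analyses". These sentences mainly say that the node-negative and node-positive cohorts are analysed together. They do not themselves define an estimator.

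**Test.** Section 12, Primary objective: "We will use the matched pair Durkalski's test (36), accounting for the cluster-correlation within subjects". The Synopsis names the same test for both sensitivity and specificity.

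**What is absent.** Section 12 promises 95% confidence intervals for all estimates but gives no method for them. Neither the Synopsis nor Section 12 gives a formula for the difference between tracers, defines a subject-weighted difference, or notes that the test and a pooled proportion weight subjects differently. The citations do not fill the gap: the numbers attached to the test and its R package lead, in the reference list, to a cetuximab-dye study and to the 1947 McNemar paper.

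**The concern.** For subject k, let n_k be the eligible nodes (histologically positive for sensitivity, negative for specificity). Let b_k be the nodes that only the zirconium scan classifies correctly and c_k those that only FDG classifies correctly. The pooled difference is Σ(b_k − c_k)/Σn_k. Durkalski's chi-square is [Σ(b_k − c_k)/n_k]² / Σ[(b_k − c_k)/n_k]². Its numerator is the unweighted sum of subject-level differences, so a subject with one positive node counts as much as a subject with twenty.

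This is not about variance. The test does allow for correlation within subjects. The issue is which difference is tested, and a cluster-adjusted interval around the pooled difference would still describe a different quantity from the p-value.

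Sensitivity is the more exposed comparison. Subjects with no positive node drop out, and the Schema says the two-cohort structure exists to secure positive nodes, so most should come from the 7 node-positive subjects. Dependence on node count is plausible but not certain: cohort assignment uses existing imaging, and FDG-PET precedes enrolment. A discordant positive node in a clinically node-negative subject, who has few such nodes, may therefore tend to be one that FDG missed.

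At stake is the headline result, a pair of pooled proportions with a p-value that a reader will take as a test of their difference.

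**Working it through.** **1. The plan's own figures.** Inputs from Section 12: 14 subjects, 30 nodes each on average, intra-class correlation 0.005, prevalence 7.5%, discordant proportion 0.3.
- Effective sample size: 420/(1 + 29 × 0.005) = 366.8, which matches the stated 367.
- One-sided exact McNemar power is 71.4% with 27 positive nodes (367 × 0.075) and a 0.25 difference (stated: above 71%). It is 95.3% with 339 negative nodes (367 × 0.925) and a 0.1 difference (stated: above 95%).

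The figures reproduce. They come from McNemar's test on a count of nodes, so the power section also thinks in node-level differences. It uses the average of 30 nodes and says nothing about variation.

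**2. Expected nodes.** 420 × 0.075 = 31.5, about 31 positive; 420 × 0.925 = 388.5, about 389 negative.

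**3. Equal counts.** If every n_k equals n, the factor 1/n cancels from Durkalski's ratio, leaving [Σ(b_k − c_k)]²/Σ(b_k − c_k)². The test and the pooled difference then agree exactly.

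**4. Sensitivity, constructed case.** Seven subjects, n = 1, 2, 2, 2, 2, 2, 20 (total 31). b = 1 in each of the first six; c = 8 in the last.
- Pooled difference: (6 − 8)/31 = −6.5 points.
- Subject differences: 1, five of 0.5, and −8/20 = −0.4. Sum 3.1, mean 3.1/7 = +44.3 points.
- Durkalski: 3.1²/(1 + 5 × 0.25 + 0.16) = 9.61/2.41 = 3.99, p = 0.046.
- Node-weighted clustered test: (−2)²/(6 × 1 + 64) = 4/70 = 0.057, p = 0.81.

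**5. Specificity, constructed case.** Fourteen subjects, 389 nodes: ten with n = 12, b = 2, c = 0; four with n = 67, 67, 67, 68, b = 0, c = 8.
- Pooled difference: (20 − 32)/389 = −3.1 points.
- Subject sum: 10 × 2/12 − 3 × 8/67 − 8/68 = 1.191; mean 1.191/14 = +8.5 points.
- Durkalski: 1.191²/0.3344 = 4.24, p = 0.039.
- Node-weighted clustered test: (−12)²/(10 × 4 + 4 × 64) = 144/296 = 0.486, p = 0.49.

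**6. How often.** Simulation at 0.3 discordance, 3,000 trials per setting. Node counts are assumed: Poisson with gamma variation between subjects, relative variance 0.2 to 1 for specificity and 0.5 to 1 for sensitivity. Opposite sign means that the pooled difference and the subject mean point in different directions.
- Equal counts: never opposite, and verdicts always agree.
- Specificity, 14 subjects: opposite in 14–27% of trials with no true difference, 4–13% at 0.05, 0–3% at 0.1.
- Sensitivity, 7 subjects: about 13% with no difference, 9% at 0.1, under 1% at 0.25.
- Specificity, with the tracer difference assumed to fall as node count rises (0.05 at the average count, relative variance 0.5): opposite in 14–61%, but significant on Durkalski's test and opposite in only 0.1–0.3%.

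**The case against.** Several points against the concern are sound.

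*The pooling sentence does not set the estimator.* A reader might take the Synopsis sentence as proof of node weighting. It mainly says that the cohorts are combined. The node-level unit is a fair inference from Section 10.1 and the sample size paragraph, but no formula is written. The mismatch is therefore conditional on the pooled proportions being what is reported beside the p-value.

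*Disagreement in sign is not a common outcome.* A reader might infer from the constructed cases that test and estimate will often point in opposite directions. The chi-square has no sign; only its numerator does. With 31 positive nodes split 1 to 7 across seven subjects and one in each of three others, and the same discordance in every subject, opposite signs occur in 16% of trials with no true difference. There both quantities are noise around zero. The figure falls to 0.9% at the planned 0.25 difference, and no such trial was significant on either test. The case in step 4 is also more discordant than the plan assumes: 14/31 = 45% against 0.3.

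*Differing verdicts do not measure the mismatch.* In that same simulation at 0.25, Durkalski's test and the node-weighted test reach different verdicts in 16% of trials (power about 48% and 56%). Because the discordance was equal in all subjects, both tests target the same difference. The gap is one of efficiency between two valid tests.

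*Durkalski's test is not wrong.* A reader might conclude that it should be replaced. Equal subject weighting is a legitimate choice, and it protects against one subject dominating. With 20 of 31 positive nodes in one subject (n = 1, 1, 1, 2, 2, 4, 20), its power at 0.25 is about 13%, against 4% for the node-weighted test.

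What survives is that the plan names a test of one quantity, describes estimates of another, and defines neither the difference nor its interval.

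**Conclusion.** The point holds in a limited form. With unequal node counts and a tracer difference that depends on node count, Durkalski's p-value does not test the node-pooled difference. The gap can be large in a constructed case (−6.5 against +44.3 points for sensitivity, −3.1 against +8.5 for specificity, with p = 0.046 and 0.039). These cases show what is possible, not what is expected.

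The conclusion rests on three things: pooled node proportions are reported, node counts vary between subjects, and the tracer difference varies with count. The first follows from Sections 10.1 and 12. The second is likely for about 31 positive nodes drawn mainly from one cohort. The third is plausible but undocumented. All node-count distributions used here are assumptions. The documents do not support a claim that the primary test is invalid or that sign reversals with significance are to be expected.

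It is still worth settling before analysis, because the Synopsis commits to testing at 0.05 and interpreting intervals, and the p-values will be read beside the pooled proportions.

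**What to change.** In the Synopsis and Section 12:

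1. Keep Durkalski's test. Beside each of its p-values report the mean over subjects of (b_k − c_k)/n_k with a subject-level 95% CI, and state that this is the difference being tested. Say that subjects with no eligible node are excluded, and give their number.
2. Label the pooled sensitivity and specificity as node-weighted, and give them subject-clustered 95% CIs by a named method.
3. Pre-specify the node-weighted clustered test, Z = Σ(b_k − c_k)/√Σ(b_k − c_k)², as a sensitivity analysis and not as a replacement. Its weakness when one subject holds most of the positive nodes is the reason not to promote it.

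The cost is some wording, a little extra analysis and one more reported quantity. No data collection changes. Fixing the roles of the two tests in advance also removes any later choice between two verdicts.
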